5.1 Primary Outcome Measures

- Overall postoperative morbidity rates

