8.1.2 Incidence of postoperative complications

The number of all patients treated with surgery as the denominator and the number of the patients with any intraoperative and postoperative complications as the numerator are used to calculate the proportions.

8.1.3 Incidence of overall postoperative complications: The postoperative complication criteria refer to short-term complications after surgery in the postoperative observation project. The time is defined as within 30th after surgery, or the first discharge time if the days of hospital stay more than 30 days.

8.1.4 Incidence of postoperative major complications: The standard for postoperative major complications refers to the short-term complications in the postoperative observation project. according to the Clavien–dindo grade, IIIA level and above for serious complications, and when multiple complications occur simultaneously, the highest ranked complication is the subject.

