9.3.1.9 Regulations Regarding Gastric Canal and Peritoneal Drainage Tube

Whether the gastric canal or peritoneal drainage tube is left after surgery is determined by experience and actual needs and is not specified in this study protocol, and record the reasons in the CRF.

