9.3.3.3 Post-operative rehabilitation management

Management methods of incision, stomach and abdominal drainage tube: Follow regular diagnosis and treatment approaches. Eating recovery time, diet transition strategies: Follow regular diagnosis and treatment approaches.

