Internal hernia	Postoperative CT findings of cystic or cystic and solid mass, and intestinal aggregation, stretching, translocation, abnormal mesenteric movement, and thickening of the blood vessel.
Alkaline reflux esophagitis	1. Endoscopic examination and biopsy of the upper gastrointestinal

	tract showed evidence of inflammation of the mucous membranes and gastrointestinal metaplasia; 2. CT scan and gastrointestinal barium meal examination showed no expansion or obstruction of the input loop.
Incision splitting	Including partial dehiscence of the incision and full-layer dehiscence
Incisional hernia of abdominal wall	The swelling tumor showing in the surgical scar area or abdominal wall swelling when standing or force. CT shows ventral wall continuity interruption and hernia content extravasation
Incision infection	Thickening of the soft tissue at the incision, in or below the incision of gas, exudation, swelling of the incision or pus from the incision extrusion, or secretion culture of pathogenic bacteria.
Lymphatic leakage	A chyle test when abdominal drainage fluid exceeded 300 ml/day for 5 consecutive days after postoperative day 3.
Pneumonia	Complies with one of the following two diagnostic Criteria: 1. Auscultation/percussion voiced + one of the following: fresh sputum or sputum character changes; blood culture (+); bronchoalveolar lavage fluid, anti-pollution sample brush, biopsy specimens cultured pathogenic bacteria. 2. Chest film hints of new or progressive infiltration + one of the following: fresh sputum or sputum character changes, blood culture (+), bronchoalveolar lavage fluid, anti-pollution sample brush, biopsy specimens cultured pathogenic bacteria; isolate virus or detect IgM, IgG (+) of respiratory viral
Acute pancreatitis	Irritability, abdominal pain, anti-jumping pain, fever, leukocyte increase and blood amylase increased occurring and diagnosed by ultrasound or CT within 3 days after surgery.
Acute cholecystitis	Serum bilirubin exceeding 85 μ mol/l and ultrasound examination shows gallbladder enlargement, wall thickness, signal and sound shadow of gallbladder stone, bile internal sediment, gallbladder contraction bad etc.
Pleural effusion/infection	CT scan showed the localized fluid low density area of thoracic cavity, which could accompany with gas, and culture pathogenic bacteria in thoracic endocrine.

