Abdominal infection	There is at least one of the following evidences in abdominal cavity within 30 days after operation: 1. discharge of pus, with/without microbiological examination; 2. bacterial culture positive; 3. diagnosed by detection, pathology, imaging findings.

Study protocol

Pelvic infection	Symptoms of systemic infection or rectal irritation, combined with a rectal finger examination and touching tenderness, or a married woman with a posterior vault to extract pus-based fluid
Sepsis	The following two conditions are available: 1. There is evidence of active bacterial infection, but the blood culture does not necessarily appear pathogenic bacteria; 2. meeting two of the following four items at the same time: (1). body temperature $>39.0^{\circ}\text{C}$ or $<35.5^{\circ}\text{C}$ for 3 consecutive days, (2). heart rate >120 times/min; (3). total white blood cells $>12.0 \times 10^9/\text{L}$ or $<4.0 \times 10^9/\text{L}$, wherein neutrophils >0.80 , or naïve granular cells >0.10 ; (4).Respiratory frequency >28 times/min
Urinary system infection	Symptoms of urine frequency, urgency and urine pain etc. and urine bacteria culture colony count 1000~10 million/ml in the absence of antibiotics; No symptoms of urine frequency, urgency and urine pain etc, urine bacterial culture colony count $\geq 100,000/\text{ml}$
Pancreatic fistula	The level of amylase in the drainage fluid is three times than normal level.
Bile fistula	Symptoms of abdominal distension, Abdominal pain, tenderness, anti-jumping pain, muscle tension, abdominal puncture or drainage fluid for bile
Celiac fistula	The drainage fluid is milky white, and more than 200ml/d and does not decrease for 48 hour, the celiac qualitative test is positive, and the level of triglyceride >110 mg/dL at the same time.
Nutritional disorder after gastrectomy	In the presence of weight loss, anemia, malnutrition bone disease, vitamin A deficiency and other symptoms, laboratory tests suggest that the intestinal absorption function test is abnormal, excluding other causes of nutritional disorders
Bone disease after gastrectomy	Lumbar back pain, length shortening, kyphosis, bone fractures and other symptoms. Bone density decreased combining with elevated alkaline phosphatase and serum calcium reduction, the concentration of serum 25-(OH) D3 and 1,25-(OH) 2D3 increasing and the serum parathyroid hormone increasing. Exclusion of bone disease caused by other causes.

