DIC	1. There are basic diseases easily leading to DIC, 2. There are more than two clinical performances: (1) severe or multiple bleeding tendencies; (2) Microcirculation disorder or shock cannot be explained by the original disease. (3) Extensive skin mucosal embolism, focal ischemic necrosis, shedding and ulcer formation, or unexplained lung, kidney, brain and another organ failure. (4) anticoagulant treatment is effective. 3. The laboratory meets the following conditions: (1) there are 3 or more experimental abnormalities: platelet count, prothrombin time, activated partial coagulation enzyme time, thrombin time, fibrinogen level, D-two poly, and (2) difficult or special cases for special examination.

Other	Complications other than the above complications, which do not exist before surgery but appear after surgery
-------	--

(1) Blood test items (At postoperative day 1, 3, 5)

Peripheral blood routine assessment: Hb, RBC, WBC, LYM, NEU, NEU%, and PLT、 MONO;

Blood biochemistry: Albumin, prealbumin, total bilirubin, AST, ALT, creatinine, urea nitrogen, fasting blood glucose, potassium, sodium, chlorine, calcium, CRP, IL-6, PCT, Blood amylase, ascites amylase.

(2) Postoperative rehabilitation evaluation:

Time to first ambulation (hours), time to first flatus (hour), time to liquid diet, time to removal of gastric tube (d), daily volume of gastric drainage (ml), time to removal of abdominal drainage tube (d), daily volume of drainage (ml).Blood transfusion volume (ml) from the end of surgery to postoperative discharge: a transfusion event is defined as infusion of the red blood cell suspension (ml) or whole blood (ml).Postoperative hospital stays (days): periods form surgery day to first discharge day

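### Pancreatic fistula is scored from drain amylase alone while drains are optional, so part of the primary morbidity rate depends on whether a drain was left

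*Protocol*

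**What the plan says.** The primary outcome (Protocol, 5.1) is "Overall postoperative morbidity rates". Section 8.1.3 links it to the complication table in 9.3.4: "The postoperative complication criteria refer to short-term complications after surgery in the postoperative observation project". The window is 30 days, or the first discharge for longer stays. No minimum grade is set, and Clavien-Dindo grade I, as given in 9.3.4, includes deviations that need no specific treatment.

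For pancreatic fistula the table's full criterion is "The level of amylase in the drainage fluid is three times than normal level". It states no day, no clinical effect, no reference for the normal level (serum or laboratory limit) and no source other than drainage fluid. The laboratory list in 9.3.4 for postoperative days 1, 3 and 5 ends with "Blood amylase, ascites amylase". It does not say what applies when there is no drain.

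On drains, 9.3.1.9 says "Whether the gastric canal or peritoneal drainage tube is left after surgery is determined by experience and actual needs", and 9.3.3.3 says "Management methods of incision, stomach and abdominal drainage tube: Follow regular diagnosis and treatment approaches". The reasons for the drain decision go on the CRF (9.3.1.9), and 9.3.4 records removal time and daily volume. Section 3 describes a single-centre, non-randomised, open, non-inferiority study.

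**The concern.** Whether a patient can have this primary-outcome component at all depends on a discretionary decision taken by staff who know the arm. Take two patients with the same uneventful recovery and the same transient amylase rise. The drained one is a primary event; the undrained one is not.

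Two consequences follow. If drain use or duration differs between arms, some of the recorded difference in morbidity reflects detection and not surgery, in either direction. If drain use is the same, symptom-free events are added to both arms. That shrinks a true difference, which in a non-inferiority comparison works towards the favourable conclusion, and it adds variance.

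This is not a detail left to a statistical analysis plan: the event definition is fixed in the protocol.

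**Working it through.** **Neighbouring rows of the table (9.3.4).** Bile fistula lists symptoms and accepts abdominal puncture as well as drainage fluid. Acute pancreatitis needs symptoms plus ultrasound or CT within 3 days. Abdominal infection has a 30-day window and can be shown by culture or imaging. The pancreatic fistula row has none of these features.

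**The plan's own figure.** Section 3.3 gives 68 per group for 15% versus 15%, margin 15 points, α = 0.05, power 80%. Exact binomial enumeration of the unpooled Z test at one-sided 0.05 gives power 0.8003 at 68, the smallest size from 60 upward to reach 80%. The final 75 is 68 × 1.1 = 74.8, rounded up. By the unpooled normal formula used below, power at 68 is 79%. The concern does not rest on these figures; they set the scale.

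**Model.** Let b be the probability that a drained, otherwise uncomplicated patient is positive on amylase alone, and d the share drained. With 15% morbidity from all other causes in both arms:

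recorded rate = 0.15 + 0.85 × b × d

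artefact = 0.85 × b × (d robotic − d laparoscopic)

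Neither b nor d is in the documents; all values below are assumptions.

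**Unequal drain use, 90% robotic and 60% laparoscopic:**

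| b | Robotic | Laparoscopic | Artefact (points) | Power at 68 per group |
|---|---|---|---|---|
| 2% | 16.5% | 16.0% | +0.5 | 74% |
| 5% | 18.8% | 17.6% | +1.3 | 67% |
| 10% | 22.7% | 20.1% | +2.6 | 55% |

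For example, 0.85 × 0.10 × 0.30 = 0.0255. Power = Φ[(0.15 − difference)/SE − 1.645], with SE = √{[pR(1 − pR) + pL(1 − pL)]/68}. Reversing the imbalance reverses the sign: −0.5, −1.3 and −2.6 points, in favour of the robotic arm.

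**Larger inputs.** With b = 30% and 100% versus 70% drained: 0.85 × 0.30 × 0.30 = 0.0765, or 7.7 points.

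**Equal drain use.** If a share q = b × d of otherwise uncomplicated patients is positive in both arms, a true difference D is recorded as (1 − q) × D. With everyone drained, a true 15-point excess is recorded as 0.98 × 15 = 14.7 points at b = 2% and 0.90 × 15 = 13.5 points at b = 10%. The recorded rates are then 16.7% and 23.5% in both arms, and power with no true difference is 76% and 66%.

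**The case against.** **Bias between arms is not shown.** A reader might infer that one arm is favoured. The documents do not support that. This is one centre, every surgeon must be experienced in both techniques (7.1), and a surgeon's drain habit may apply equally to both arms. No section suggests that drain use differs by arm. This stands: the open, non-randomised design permits an imbalance but does not establish one.

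**A large artefact is not shown.** A reader might take 7.7 points, about half the margin, as the likely size. It comes from one high combination of assumed inputs. The lower range gives 0.5 to 2.6 points, also on assumptions.

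**The rate need not exceed the planned 15%.** The studies behind that figure are not described and may already count amylase-defined fistulas. The model assumes that they do not. This stands as a caveat on the recorded rates.

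**The protocol already limits the problem.** Section 8.1.4 defines major complications from grade IIIa upward, which leaves out symptom-free amylase findings. A clinically evident leak without a drain can be counted as abdominal infection or under 'Other'. Planned sampling is on three days, even though the criterion names none. These points reduce the dependence. They do not remove it, because a silent rise counts only where there is a drain and the primary has no grade limit.

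**The chyle entries are not the same problem.** Lymphatic leakage ("A chyle test when abdominal drainage fluid exceeded 300 ml/day for 5 consecutive days after postoperative day 3") and the milky-fluid fistula also need drain output and use different thresholds. A reader might infer volume-only events or double counting. Both entries involve a chyle test, the second also requires a triglyceride level, and the numerator counts patients, so two labels do not count one patient twice.

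**Conclusion.** The point holds as a modest flaw in how a primary component is ascertained. As written, a symptom-free amylase rise is a primary event in a drained patient and cannot be one under this criterion in an undrained patient.

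The size cannot be derived from the documents. Under 2% to 10% amylase-only positivity and a 30-point drain imbalance, the artefact is about 0.5 to 2.6 points against the 15-point margin; only much larger assumed inputs bring it to 7.7. These figures also assume 15% morbidity from other causes in both arms and the same underlying risk with and without a drain. With equal drain use there is no artefact, only dilution by the factor (1 − q) and some loss of power. The documents support neither a claim that the comparison is biased nor a claim about its direction.

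**What to change.** 1. Reconcile the fistula criterion in 9.3.4 with the sampling days and with the optional drain in 9.3.1.9 and 9.3.3.3, including what applies to a patient without a drain. Which clinical definition to use is for the investigators.
2. Report the share of patients drained and the drain duration by arm.
3. List fistulas diagnosed on amylase alone (no treatment given, Clavien-Dindo grade I) separately by arm.
4. Pre-specify a sensitivity analysis of the primary non-inferiority comparison that excludes those fistulas.
5. As a secondary matter, reconcile the lymphatic leakage and milky-fluid entries.

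The cost is wording in the complication table, one table and one analysis. Drain reasons, removal time and volume are already recorded, and severity grading is already required. The downside is that grade depends on treatment decisions made in an unblinded study. Moving the primary itself to a higher grade for drain-defined items would bring that discretion into the main result, so the restricted analysis should be supportive and not replace the primary.

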9.4 Follow-Up

9.4.1 Follow-up Period and strategy

Follow-up visits will be completed by special persons for all cases selected in this study .All patients are followed up with 30 days, Recommend patient follow-up every 3 months during the first 2 years and then every 6 months beyond the third year (1、 3、 6、 9、 12、 15、 18、 21、 24、 30 and 36 months after the operation),and record with patients’ consent. This study suggests that the above examinations should be conducted in the patient's primary surgical research center, but does not exclude outer court review. For Outer Court review, It recommended that visiting the hospital as a three-level hospital, and these information will be recorded by the follow-up specialist. The occurrence of tumor recurrence or metastasis and the survival status of all patients are evaluated and recorded according to the results of the various examinations. Patients who refuse to follow the protocol should be recorded as lost to follow-up, and at the end of the study, these cases should be analyzed together with cases lost to follow-up in line with the criteria of this study.

9.4.2 Assessment items during the follow-up

(1) Systematic physical examination:

The doctor in charge will regularly conduct a systematic physical examination at the time of each follow-up, giving particular attention to superficial lymph nodes, abdomen, and signs of metastases, among others. Meanwhile, ask about general conditions (Height, weight, BMI, diet).

(2) Blood test items:

Peripheral blood routine assessment: Hb、 RBC、 WBC、 LYM、 NEU、 NEU%、 PLT、 MONO

Biochemistry: Albumin, pre-albumin, total bilirubin, Indirect bilirubin, direct bilirubin, AST, ALT, creatinine, urea nitrogen, Total cholesterol, triglycerides, fasting blood glucose, potassium, sodium, chlorine, calcium, serum tumor markers: CEA 、 CA19-9、 CA72-4、 CA12-5、 AFP.

(3) Imaging items:

Recommend patient take imaging examination every 3 months during the first 2 years and then every 6 months beyond the third year (1、 3、 6、 9、 12、 15、 18、 21、 24、 30 and 36 months after the operation). Including: Whole abdomen (including cavity) CT (thickness of 10 mm or less, in case of contrast agent allergy, CT horizontal scanning is only allowable or conversion to MRI). Upper gastrointestinal endoscopy (histopathological biopsy, endoscopic ultrasonography when necessary). Chest X-ray (AP and lateral views): lung field condition. Other means of evaluation: gastrointestinal radiography, ultrasonography of other organs, whole body bone scanning, and PET-CT, among others used at physician's discretion.

9.5 Post-operative adjuvant therapy

9.5.1 Indications for postoperative adjuvant chemotherapy

After completion of the surgical treatment, according to the postoperative pathological results, subjects among the R0 resection cases that are stage II and above are administered postoperative adjuvant chemotherapy according to the provisions of this program.

For cases of non-R0 resection or recurrence after R0 resection, this study does not

stipulate the follow-up treatment plan; the research center decides on the action to be taken according to the clinical treatment routine.

9.5.2 Postoperative adjuvant chemotherapy

This study uses a combination of chemotherapy based on 5-FU (5-fluorouracil) and recommends the SOX regimen.

In cases of good physical and tolerable conditions, chemotherapy is first started within 3-4 weeks after surgery and then according to the regularity of the chemotherapy cycle.

During the chemotherapy period, tumor recurrence should be assessed according to the follow-up plan.

When tumor recurrence occurs during chemotherapy, the adjuvant chemotherapy regimen of this study is discontinued. The follow-up treatment is decided by the research center according to the clinical treatment routine. This study does not make regulations, but the cause and follow-up treatment plan should be recorded in the CRF.

Adjuvant chemotherapy requires written approval from the patient.

Subjects that refuse postoperative adjuvant chemotherapy or do not complete the adjuvant chemotherapy are not excluded from this study, but the cause is marked and recorded in the CRF.

Patients who choose adjuvant chemotherapy, irregular chemotherapy, or a non-first-line regimen are not excluded from the study, but Safety Evaluation Committee is obliged to monitor patient safety during follow-up. The patient's chemotherapy medication must be recorded in the CRF.

9.5.3 Safety Evaluation Indicators of Postoperative Adjuvant Chemotherapy

The safety evaluation indicators for patients enrolled in the study should be immediately filled out by the investigators before and after each postoperative adjuvant chemotherapy cycle, with specific items including the following:

- (1) Performance Status (ECOG)
- (2) Subjective and objective status (according to the records of CTCAE v3.0 Short Name)
- (3) Blood tests:

Peripheral venous blood assessment: Hb, RBC, WBC, LYM, NEU, NEU%, PLT, MONO.

Blood biochemistry: albumin, prealbumin, total bilirubin, AST, ALT, creatinine, urea nitrogen, fasting blood glucose, serum tumor markers (CEA, CA19-9, CA72-4, CA12-5, AFP)

- (4) Safety evaluation items to be implemented during chemotherapy when necessary (refer to CTCAE v3.0):

Neurotoxicity

Cardiovascular system (cardiac toxicity, ischemic heart disease, etc.)

Bone marrow suppression and infections due to immune dysfunction

Others

10 Statistical analysis

10.1 Statistical analysis plan

- Statistical software: we will use SPSS statistical software, version 23.0 (SPSS Inc), and the R software environment (R Foundation for Statistical Computing) to perform statistical analyses.
- Basic principle: The method of differential testing was adopted. The safety population of the study consists of the patients who receive safety evaluation data after the intervention. Descriptive statistics and two-sided tests were conducted for the safety indicators and the incidence of adverse reactions. A p-value <0.05 is considered statistically significant. The confidence interval of the parameters is estimated with a 95% confidence interval.
- Shedding analysis: Total shedding rate of two groups and loss rate due to adverse events will be compared using pearson χ^2 test

- All data analyses will be conducted on a per-protocol (PP) basis.
- Method of outlier determination: the observation value is greater than P75 or less than P25, and the exceed value more than 3 times of the quartile spacing ($=p75-p25$), which will be sentenced to outlier data. During the analysis, the sensitivity analysis is used for outlier data, namely analyzing outcomes including or excluding outlier's data. and if the results are not contradictory, the data is retained; if the contradiction, it depends on the specific circumstances.
- Descriptive statistics: The measurement data gives the mean, the standard deviation and the confidence interval, and the minimum value, the maximum value, the P25, the median and the P75 are given when necessary; matched data also gives the mean and standard deviation of the gap-value, and the median and average rank of the Non-parametric method. The nominal-scale data gives the frequency distribution and the corresponding percentages. The level data gives the frequency distribution and the corresponding percentages, as well as the median and the average rank. Qualitative data give positive rate, positive number, and denominator numbers. The survival data gives the number of events, the number of deletions, the median survival time, and the survival rate.
- Subgroup analysis : Sub-group analysis is to find the factors that may affect prognostic according to the specific circumstances of the data.
- Missing values handling: This study does not fill in missing values
- Safety analysis: counting adverse responds incidence and incidence of adverse events and make a list to describe the adverse events occurring in the study. describe the results of the laboratory tests before and after the normal/abnormal changes and the relationship between the abnormal changes and drugs in the research, and make a list on the "normal/abnormal" changes occurred in the study.. More detailed statistical analysis is shown in the statistical analysis plan.

11 Data management

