Outcome Measures	
Primary Outcome Measures :
 
 ● Overall postoperative morbidity rates 
Secondary Outcome Measures :
 
 ● Intraoperative morbidity rate ● Operative time ● Estimated blood loss ● Number of harvested and metastatic lymph nodes ● the lengths of incision, proximal and distal margins ● Time to first flatus ● Time to first liquid diet ● Postoperative hospital stay ● Total cost
Statistical considerations	
All data analyses will be performed using SPSS statistical software, version 23.0 (SPSS Inc), and the R software environment (R Foundation for Statistical Computing).
 
All data analyses will be conducted on a per-protocol (PP) basis. This study does not fill in missing values. Normally distributed continuous variables will be presented as mean and standard deviation and compared using the t-test if normally distributed, or as median and interquartile range and compared using the Wilcoxon rank-sum test if non-normally distributed; while categorical data will be presented as number and percentages and compared using the Pearson χ^2 test or the Fisher exact test, as appropriate. Sensitivity analysis is used for extreme outlier data. The confidence interval of the parameters is estimated with a 95% confidence interval. The central effect analysis and subgroup analysis are conducted according to the specific situation. All the statistical tests were tested by two sides. A p-value <0.05 is considered statistically significant.

1. Research background

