
to conduct clinical research on robotic-assisted radical gastrectomy with D2 lymphadenectomy for locally advanced gastric cancer. At present, there is no prospective study report on the treatment of locally advanced gastric cancer with robot and laparoscopic D2 lymph node dissection.

Our center reported the first robotic-assisted gastrectomy in China in 2010, and has completed more than 600 cases of robotic-assisted gastrectomy. At present, there is a lack of prospective research literature reports on robot and laparoscopic radical total gastrectomy combined with D2 lymphadenectomy in the treatment of locally advanced gastric cancer, and the safety and effectiveness of robotic and laparoscopic radical total gastrectomy with D2 lymphadenectomy for locally advanced gastric cancer are still unclear. This study intends to conduct the first international prospective study of robot and laparoscopic radical total gastrectomy with D2 lymphadenectomy for the treatment of locally advanced gastric cancer, and to provide evidence-based medicine for the widespread development of robot-assisted total gastrectomy for locally advanced gastric cancer.

2. Objective

The purpose of the prospective trial is to investigate the safety and feasibility between Robotic and laparoscopic radical total gastrectomy with D2 lymphadenectomy for locally advanced gastric cancer.

3. Research design

prospective, single-center, non-randomized, controlled, non-blind, and non-inferiority observation trial

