3.3 Estimate sample size

This study is a non-inferiority study, with postoperative complications as primary outcome. According to the relevant studies, the postoperative complication rate of laparoscopic total gastric surgery is about 15%. In this study, it was assumed that the

postoperative complication rate of the study group was similar to the control group, with $\alpha=0.05$, $\beta=0.2$, and the non-inferiority threshold value set as 15%. PASS 11 was used for calculation, and the sample size of each group was 68 cases. Considering that the maximum detachment rate of this clinical study was 10%, the final sample size was 75 cases in each group.

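### A trial designed and sized for non-inferiority is given two-sided difference tests, and its 95% confidence interval is neither tied to the 15-point margin nor matched to the sample size

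*Protocol*

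**What the plan says.** The design is stated consistently. Section 3 (Research design), like the Summary, calls the study a "prospective, single-center, non-randomized, controlled, non-blind, and non-inferiority observation trial". Section 3.3 says "This study is a non-inferiority study, with postoperative complications as primary outcome". It assumes that "the postoperative complication rate of laparoscopic total gastric surgery is about 15" per cent, that the robotic rate is similar, that α = 0.05 and β = 0.2, "and the non-inferiority threshold value set as 15" per cent. This gives 68 per group, or 75 after allowing for 10% dropout. The sidedness of α is not stated.

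The analysis text takes another line. Under its basic principle, section 10.1 says "The method of differential testing was adopted". In the Summary (Statistical considerations), "categorical data will be presented as number and percentages and compared using the Pearson" chi-square test or Fisher's exact test, and "All the statistical tests were tested by two sides. A p-value <0.05 is considered statistically significant". On intervals, section 10.1 says only that "The confidence interval of the parameters is estimated with a 95% confidence interval"; the Summary repeats this.

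The margin appears in the sample-size text and nowhere in the analysis text. Section 10.1 closes by referring further detail to a separate SAP, which is not at hand.

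**The concern.** The primary endpoint, overall postoperative morbidity, is a proportion of patients, so the general rule for categorical data covers it. A chi-square or Fisher test takes equal rates as its null hypothesis. A non-inferiority trial must instead reject the hypothesis that the robotic rate exceeds the laparoscopic rate by 15 points or more. A non-significant difference test does not do that, and the smaller the trial, the easier non-significance is to obtain.

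The planned confidence interval is the one stated tool that could answer the question, but the protocol ties it to no decision. If it were used, its level would matter. A 95% interval corresponds to a one-sided 0.025 test, whereas the sample size appears to rest on one-sided 0.05. What is at stake is whether a safety comparison can conclude non-inferiority on evidence that does not support it, and whether the stated 80% power is real for the interval the protocol names.

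**Working it through.** **Inputs (section 3.3).** Both rates p = 0.15; margin Δ = 0.15, read as absolute points; α = 0.05; power 80%; equal groups; n = 68 before dropout and 75 after.

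**Step 1: reproduce 68.** The rule is: declare non-inferiority if d + z·SE < 0.15. Here d is the robotic rate minus the laparoscopic rate, SE = √{[p₁(1−p₁) + p₂(1−p₂)]/n}, and z = 1.645 (one-sided 0.05, 90% interval) or 1.960 (one-sided 0.025, 95% interval). Summing exact binomial probabilities over all outcomes with both true rates at 15% gives the power:

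| n per group | 90% interval | 95% interval |
|---|---|---|
| 68 | 80.0% | 70.1% |
| 75 | 82.4% | 73.0% |
| 89 | 87.8% | 80.1% |

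The smallest n reaching 80% is 68 at one-sided 0.05 and 89 at one-sided 0.025.

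**Step 2: cross-check with the closed form,** n = (z₁₋α + z₀.₈)² · 2p(1−p)/Δ².
- One-sided 0.05: (1.645 + 0.842)² × 2 × 0.15 × 0.85 / 0.15² = 70.1.
- One-sided 0.025: (1.960 + 0.842)² × 2 × 0.15 × 0.85 / 0.15² = 88.95, so 89.

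Farrington-Manning gives 74.4 and 94.8. A variant with the null variance taken at p ± Δ/2 gives 68.0 and 86.2. None of the methods tried reaches 68 at one-sided 0.025. The plan's figure is therefore reproducible, but as a one-sided 0.05 calculation.

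**Step 3: what the difference test would allow.** Set the true rates at 30% robotic and 15% laparoscopic, exactly at the margin. The chance of each result is:

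| Rule | n = 68 | n = 75 |
|---|---|---|
| Two-sided chi-square not significant at 0.05 | 43.8% | 39.9% |
| Upper limit of 90% interval below +15 points | 5.4% | 5.2% |
| Upper limit of 95% interval below +15 points | 2.7% | 2.6% |

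The two interval rules stay near their nominal 5% and 2.5%. Reading non-significance as non-inferiority does not.

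**Step 4: two possible results at 68 per group.**
- 18/68 against 10/68: difference +11.8 points, chi-square p = 0.09, 95% interval −1.7 to +25.2. There is no significant difference, yet the upper limit is well beyond the margin.
- 12/68 against 10/68: difference 0.1765 − 0.1471 = 0.0294, SE = 0.0631, chi-square p = 0.64. The upper limit is 0.0294 + 1.645 × 0.0631 = 0.133 with a 90% interval (non-inferior) and 0.0294 + 1.960 × 0.0631 = 0.153 with a 95% interval (not shown). The interval level alone decides the conclusion.

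**The case against.** The strongest reply is that the protocol defers detail to a SAP. The primary decision rule, the interval method and the link from interval to margin are commonly placed there, and silence on them would be no fault. The wording can also be read narrowly: the basic-principle item goes on to safety indicators and adverse reactions, and the chi-square sentence does not name the primary endpoint. This does not remove the problem. The protocol is not silent; it states a method. The Summary makes all tests two-sided, and postoperative morbidity is itself a safety outcome. A SAP with a margin-based test would contradict the protocol, and one that followed the protocol would not test non-inferiority.

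Three further points stand as qualifications:
- One-sided 0.05 is inferred from reproducing 68, because the protocol gives no sidedness. A general reporting interval at 95% conflicts with that only if it is the decision interval. The 70–73% power is conditional on that use, although no other interval is named.
- The 80.0% match belongs to the simple unpooled (Wald) interval. A 90% Newcombe interval gives 78.2% at 68. The difference is about 2 points, and it does not bring a 95% interval near 80%.
- Nothing in the protocol says that p > 0.05 will be taken as non-inferiority. The 43.8% measures the risk of that reading; it does not describe a planned rule.

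**Conclusion.** The concern holds; the protocol is wrong as written and this must be fixed. The tests it states cannot answer the question it poses, and the margin that determined its size plays no part in its stated analysis. The interval level is a second mismatch. With the stated 95% interval as the decision rule, power is about 70% at 68 per group and 73% at 75, against the stated 80%; reaching 80% would take 89 evaluable per group. The figure of 68 is not itself an arithmetic error, since it follows at one-sided 0.05. These results assume a margin in absolute points, true rates of 15% in both groups for power, and an unpooled interval for the risk difference. The contradiction between design and tests depends on none of these.

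**What to change.** In the Summary (Statistical considerations) and section 10.1, state for the primary endpoint that the risk difference in overall postoperative morbidity, robotic minus laparoscopic, is estimated with a confidence interval by a named method. Non-inferiority is declared only if the upper limit is below +15 percentage points. Add that a non-significant difference test is not evidence of non-inferiority, and limit the difference tests to the secondary endpoints.

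State the sidedness of α in the Summary and section 3.3, and make the interval level agree with it, in one of two ways:
- **(a)** One-sided 0.05 with a two-sided 90% interval. This fits 80% power at 68 per group with the unpooled interval.
- **(b)** Keep the two-sided 95% interval and restate power as about 70% at 68 per group (73% at 75).

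Both are wording changes; the price of (b) is the lower stated power. Restoring 80% power under (b) would need 89/0.9 = 98.9, so 99 per group, which is 24 more than the planned 75. Removing the contradiction does not require that increase.
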